REDCap will integrate electronically with the Mosio texting platform (www.mosio.com) to facilitate the text message protocol for human subjects in the intervention group and manage survey scheduling and reminders for all participants. To this end, REDCap will push the subject's name, telephone number and date of enrollment to Mosio via REDCap's secure API. Mosio provides a secure messaging and data storage environment and has been approved for use by the University of Chicago Information Security Office. Only approved researchers in the [name] Lab will have access to data stored by Mosio and will have the ability to securely download data directly to computers within the Ob/Gyn network.

All hard copies of project materials will be stored in locked file cabinets in locked offices at University of Chicago. Servers in the University of Chicago Department of Ob/Gyn are protected through a combination of a Microsoft-based firewall technology and the physical barrier of a Linksys router that is installed between the server and its internet connection. Laptop computers used to collect data will be encrypted and password protected. All data transmitted to secure servers will be encrypted. Analytic files will either be de-identified prior to analysis or limited to the minimum amount of data necessary to accomplish the intended research purposes per the HIPAA Privacy Rule. Any analytic datasets will limit the use or disclosure of PHI to the minimum necessary, if any at all, to accomplish the intended research purposes. Only IRB-approved researchers on this protocol will have access to data. These controls meet or exceed the strictness

of practices legislated and enforced by the University of Chicago Biological Sciences Division and hospitals for protected health information.

Procedures are in place to ensure confidentiality and provide informed consent as discussed above. Numeric coding of surveys/interviews and secure containment of files that link participant's responses from PHI will also minimize this risk. Finally, the [name] Laboratory will provide a contact phone number that will be included on all study correspondence and forms. The purpose of this phone number is to provide respondents with a single number to call if they have questions about any aspect of the study.

O. Bibliography

Bibliography included in online submission, View 8.1.

P. Recruiting methods

Given the shift to telehealth appointments at UCM and shelter-in-place orders due to the COVID-19 pandemic, we will pretest a remote recruitment strategy and enroll participants for the full RCT. The following strategies will be conducted to identify eligible caregivers:

- 1. Via Epic: We will use EPIC to view the schedule of outpatient visits at University of Chicago Medicine. We will use EPIC to identify patients on the clinic schedule that reside in the ZIP code target geography. We will contact patients by sending them a text message and calling their phone numbers recorded in Epic. We will attempt to recruit these patients within one week of their outpatient or telemedicine visit using the recruitment script and screening tool approved by the IRB. Eligible patients will set up a time with study staff to go through econsent and complete the baseline survey.
- 2. Via collaboration with Clinical Research Informatics: We will work with CRI to identify eligible caregivers via a three-part process:

Step 1: The study team will generate a list of patients that have an ICD 9 or 10 code of Alzheimer's disease or a Related Dementia and identify their primary or emergency contact. The study team will do this using the SlicerDicer tool available to physicians in Epic or via a request made to the Analytic Core Request System under CRI.

Step 2: The study team will then contact the patient's primary or emergency contact to assess if they are also a patient of UCM, their caregiver status and request permission to re-contact them on the day of their next scheduled outpatient or telehealth visit (see approved Chart Review Screener Survey and Script).

Step 3: This list of eligible caregivers that have given us permission to re-contact them will be shared with CRI again. CRI will set up a data-sharing warehouse that will be continually updated so that the study team can keep track of upcoming outpatient appointments of eligible caregivers. The study team will then contact these caregivers within 1 week of their healthcare visit to assess interest in the study and proceed with screening and enrollment.

This multi-step approach is necessary to identify caregivers at the point of their own healthcare – a primary focus of this study. If a patient is eligible and interested we will set up a time to contact them for e-consent, intervention delivery and to conduct the survey within one week of their outpatient or telehealth visit. If the patient is eligible, researchers will send them an e-consent form

using REDCap that is able to be filled out online. The e-consent process is one that has been developed successfully in [name] research lab.

If we are able to safely approach patients in-person again, as we have done in prior trials in this setting, we will consecutively approach patients in the waiting rooms of the SSSC, PCG and Ob/Gyn for inclusion in the full RCT. Researchers will approach potentially eligible participants and explain that they may be eligible for a research study and, if interested, further screen for eligibility. If interested in participating and available at that time, the researcher will complete the informed consent process with the caregiver. We will also attempt to recruit individuals who are accompanying patients with dementia for their care. Potential participants will be identified using administrative data (to identify patients with a diagnosis of Alzheimer's Disease and other related dementias living in the ZIP code CommunityRx target geography) and through verifying discussions with nursing and other members of the care team, including patient service representatives and social workers. Participants who are not patients will be approached for participation in the study by:

- 3. Posting recruitment flyers in relevant waiting rooms and via social networks: We will recruit caregivers of people with dementia using recruitment flyers. These recruitment flyers include study contact information posted in relevant clinic waiting rooms and shared via social networks. Flyers also include a QR code that links to a password-protected data collection form in REDCap where interested individuals can enter information (name, phone number, preferred language and dementia caregiver status) so that we can reach out with more information about the study. We will share these recruitment flyers with relevant community groups dedicated to supporting caregivers of PWD, including the Alzheimer's Association and the South Side Healthy Aging Resource Experts (SHARE) Network, among others, and allow and encouraging caregivers who have completed participation to take recruitment flyers to share with their social networks. We will also share the recruitment flyer through various social media and other outlets. Interested caregivers will then reach out to someone on the research team for further eligibility screening. Participants who have completed the trial will receive this flyer in the mail following completion of their last survey and, if they gave us permission to recontact them, we will call them to follow up and encourage them to share their flyer with other caregivers they may know. We will also use the ITMs research profile website, https://bethenewnormal.org/, and researchmatch.org to post our study and to use it as a recruiting tool for eligible subjects (see recruitment materials uploaded to View 3.1 in AURA). To supplement this strategy, we will compensate individuals \$25 for any referred person who ultimately enrolls in this study.
- 4. Receiving patient referrals from the My Diabetes, My Community (MDMC) trial: [name] and [name] lead the My Diabetes, My Community trial a three-arm parallel pragmatic randomized controlled trial among older, predominantly African American patients with type 2 diabetes seen at the University of Chicago. A dementia diagnosis and inability to complete the study on their own are two of the exclusion criteria for the trial. During screening, it is possible for research assistants to contact patients living with dementia or their caregivers. When a patient with dementia and their caregiver are identified and screen out in the MDMC trial, there is an opportunity to ask whether they would be interested in participating in another trial they may be eligible for the CommunityRx-Caregiver trial. The MDMC research assistant would ask if the patient is interested in hearing more about a trial they may be eligible for and whether it is ok to share their phone number with the CommunityRx-Caregiver team. In receiving verbal consent to share their phone number with the CommunityRx-Caregiver team, the MDMC research

assistant will document this in the patients' screening data in REDCap and notify the MDMC Project Manager (PM). The MDMC PM will then flag this record to the CommunityRx-Caregiver PM. The MDMC PM, [name], is an active study staff on the CommunityRx-Caregiver trial. A CommunityRx-Caregiver team member will then follow-up with the patient about participating in the CommunityRx-Caregiver study.

Once their participation in the RCT (either 12-month or 3-month) is complete, certain caregivers will be approached for inclusion in a qualitative interview. Researchers will contact caregivers by email, text message and phone. Research interviewers will explain that the caregiver may be eligible for a research study and, if interested, further screen for eligibility. Recruitment scripts for the various modes of contact have been submitted for review with this protocol. If eligible, researchers will guide participants through the informed consent process as described in Section M. Informed Consent.

Q. Notification of physician

Notification of the caregiver's treating physician for permission to enroll will occur using a multipronged approach. First, we will educate all treating physicians and residents working in the target clinics about the study during the pretesting phase and give treating physicians the opportunity to opt out of study participation. Secondly, we will use these education sessions to identify how treating physicians wish to be contacted for permission (e.g., via text, email, phone, text page or through the electronic medical record system). We will use that communication as documentation of treating physician permission. Lastly, we will also educate nursing staff about the study. Nurse engagement will be helpful should we need to reach a treating physician during clinical rounds.

R. Anticipated coordination

Inter-departmental faculty coordination will be facilitated by regular research meetings attended by Drs. [name] and [name] (PIs) and other Co-Investigators and key personnel. Faculty will also regularly communicate by email and phone calls as necessary. Co-Principal Investigator [name] (Professor of Medicine) will oversee enrollment of ADRD caregivers in the Primary Care Clinic. Co-Investigator, [name] (Associate Professor of Medicine – Geriatric and Palliative Medicine) practices at the South Shore Senior Center (SSSC) and will oversee enrollment of ADRD caregivers there where many caregivers receive care. She provided a letter of support for this research. We have successfully fielded data collection efforts in both of these clinical sites as well as in the Department of Ob/Gyn.

S. Pregnancy test

Not applicable.

T. Exclusion of women, minorities and/or children

This study will not exclude women, minorities or children.

U. Drugs

No drugs will be given to subjects as part of this study.

Changes to the CommunityRx-Dementia RCT protocol since Initial IRB Approval (Excluding Personnel Changes)

Per the recommendation of The University of Chicago's Institutional Review Board, V1 of this study's protocol, approved 2/11/2019, included only the study's pre-test protocol. Following completion of the pre-test, again per the IRB's recommendation, V1 was amended for the full trial (approved 11/3/2020). The below includes The majority of differences between V1 and V10 presented above include: a) planned differences between the pre-test protocol and full trial protocol (e.g., sample size, number of follow-up surveys) and b) revisions to allow remote enrollment of participants and remote administration of the intervention (conducted in person in the pre-test protocol) due to restrictions related to the COVID-19 pandemic (declared by the United States March 2020 and lifted May 2023). All changes were approved by the Institutional Review Board.

IRB amendment 1 (5/18/2020):	 Allowed for remote protocols due to the COVID-19 pandemic, and included the following changes: Chart review procedures to allow for remote recruitment, enrollment and intervention delivery Minor edits to recruitment script related to screening using chart review Change in consent process to document informed consent using electronic consent (E-consent) in REDCap; to
	conduct for the small group of pre-test participants
IRB amendment 4 (9/3/2020)	 Allowed study team to view upcoming appointments in UCM outpatient clinics for screening purposes via Epic schedules Updated procedures with the Center for Research Informatics (CRI) Request permission to share study data with CRI to expedite recruitment in a remote setting due to COVID-19 e.g. identify primary contacts of ADRD patients who are also UCM patients CRI to set up data sharing warehouse to continually provide refreshed data on upcoming patient appointments (never implemented) Minor edits to surveys
IRB amendment 8 (11/13/2020)	 Extended the pretest to the full RCT. Extended study follow-up period to 12-months Increased number of subjects enrolled Addition of 3-month and 12-month surveys Addition of 6-month and 9-month check-ins to verify contact information is up-to-date Addition of qualitative interviews and verbal consent for these interviews Permission to collect PHI for alternate contact if study team loses contact with enrolled subject

IRB amendment 9 (1/13/2021):	Included the following change: Inclusion of non-English speakers Inclusion of Spanish translated documents Minor revisions to study surveys, recruitment script, and recruitment flyer
IRB amendment 11 (4/23/2021)	Included the following changes: • Expansion of recruitment efforts to larger geographical area; expanded zip code eligibility • Minor survey updates
IRB amendment 13 (6/23/2021)	 Included the following changes: Addition of COVID-related survey items to follow up surveys Addition of chart review screening questions Addition of study team's contact information to "The New Normal." ITM's website for research trials, researchmatch.org and similar organizations for recruitment purposes
IRB amendment 16 (9/19/2021)	Included the following change: • Addition of Care Recipient Living Situation questions to follow-up surveys
IRB amendment 20 (12/17/2021)	 Included the following changes: Revisions to the verbal consent for qualitative interviews regarding payment Addition of recruitment scripts for qualitative interviews Minor edits to the protocol to include recruitment collaboration between the "My Diabetes, My Community" Trial (IRB20-0870)
IRB amendment 21 (1/13/2022)	 Included the following changes: Addition of care recipient's gender and sex question to the 12-month survey Clarification of age criteria to specify the study is recruiting caregivers age 18 and older and caregivers age 17 and younger if they are emancipated minors under Illinois State Law (750 ILCS 30/5) Description of Mosio and NowPow data sharing
IRB amendments 22 (4/13/2022)	 Include the following changes: Updated consent form to reflect [name] updated conflict of interest statement Updated qualitative protocol to include the use of Amazon Web Services to transcribe audio recordings Minor additions to the 12-month survey

IRB amendments 26 (10/5/2022)	 The study team was awarded an administrative supplement from the NIH to enroll an additional 50 male/men caregivers with a 3-month follow-up period. Changes included: Addition of 50 men caregivers for shortened follow-up period (3-months) Addition of gender screening question New consent forms in English and Spanish for the supplement Recruitment expansion to UChicago Medicine Ingalls Memorial New recruitment flyers for additional men for the supplement Slight modification of scripts and protocol for the recruitment of additional men
IRB amendments 27 (11/28/2022)	 Include the following changes: Addition of recruitment strategy in the community Minor edits to consent documents, including an update to the study coordinator's name Minor edits to the recruitment script tailored for men caregivers in the community
IRB amendments 29 (1/5/2023)	Inclusion of the Spanish version of recruitment flyers for the administrative supplement.
IRB amendments 31 (2/17/2023)	Inclusion of a QR code on the English and Spanish versions of the supplement recruitment flyers for the community that links to a password-protected data collection form in REDCap, where interested individuals can enter their name, phone number, preferred language, and dementia caregiving status, so that they can be contacted by a staff member with more information about the study.
IRB amendments 32 (3/23/2023)	Addition of supplementary recruitment strategies including snowball recruitment and compensation of successful referrals
IRB amendments 36 (7/21/2023)	 Include the following changes: Inclusion of recruitment materials to be promoted through "The New Normal" Increase the number of participants included in the qualitative protocol for the parent trial
IRB amendments 38 (8/31/2023)	This amendment is to reach out to participants who gave us permission to re-contact them for future research, and contact them with a flyer about the SCORE Study "Social care patient-reported Outcomes Study" which aims to develop meaningful and valid patient-reported outcome measures reflecting patients' experience of social care (PROMs for social care.) UChicago staff will NOT have active involvement

	with potential participants in the SIREN SCORE study at UCSF. Any inquiries about that study will be directed to the UCSF
	study staff whose contact information is provided on the flyer.
IRB amendments 40	This amendment proposes the use of UChicago's Globus for
(9/15/2023)	secure file transfer.
IRB amendments 43	This amendment serves to remove the designation of waiver of
(11/30/2023)	consent for this study. There is no waiver of consent
	associated with this study.

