The first step in the proposed program of research is to pretest the single-blind, randomized controlled trial procedures and administration of the intervention and data collection procedures to inform the design of a larger randomized controlled trial (RCT). Given the pause of in-person medical visits and shelter-in-place orders due to the COVID-19 pandemic, we will pretest remote recruitment and consent procedures as well as remote intervention delivery. Interviewers will administer telephone or video-based surveys; self-administration of a web-based follow-up survey will also be offered. We will enroll up to 404 caregivers of people with ADRD, (both with and without unmet health-related social needs (HRSNs),10 caregivers enrolled in the remote pretest, 344 caregivers in the RCT for a 12-month follow-up, and an additional 50 male caregivers in the RCT for a 3-month follow-up. All human subjects will be consecutively screened for inclusion and enrolled

as described in Section P. Recruiting Methods. Following screening, participants will be screened for unmet HRSNs and then randomly assigned to either usual care or usual care plus CommunityRx-Caregiver. Usual care is described below in Section G. Use of Controls or Placebos.

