studies with no known adverse events or breaches of confidentiality. All data collected from human subjects will be collected using standard survey procedures. The surveys will be conducted via telephone or online. Psychological and/or emotional discomfort associated with the survey questions is possible. Subjects will be informed that they can decline to answer any question and can terminate the survey or interview at any time. Explanatory statements will be included in the surveys and interviews to help the interviewer monitor and respond appropriately to discomfort, including termination of the survey or interview if necessary. Alternatives to participation include not participating in the research; participation is completely voluntary. Additional protections against these risks are described in Sections M and N, Informed Consent and Confidentiality, respectively.

There is no direct benefit to human subjects involved in the research beyond the information provided during usual care and the CommunityRx-Caregiver intervention. Participants, however, may gain personal satisfaction in contributing to research to address the humanitarian issue of unmet needs among caregivers of PWD. Potential risks include a breach of confidentiality and are both minimal and reasonable in relation to the anticipated benefits to research participants and people with dementia.

K. Monitoring of safety

The proposed data collection presents no more than minimal risk or no more risk than is encountered in routine medical or psychological examinations. As described, no surveys will be conducted without explicit documentation of informed consent and individuals will be provided with appropriate information about confidentiality when enrolling in the study and will indicate acceptance of these risks upon consent. Because we are not proposing a multi-site clinical trial, a Phase III trial, or a drug study, this study will not employ a Data and Safety Monitoring Board. Procedures are in place to ensure confidentiality and provide full informed consent as discussed below.

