The [name] Lab has listed the Principal Investigators and study coordinator phone numbers on all study correspondence and forms. The purpose of the phone numbers is to provide respondents with a number to call if they have questions about any aspect of the study. If concerns regarding a participant's safety are endorsed within the health-related social needs screening, REDCap will deliver an alert to the research assistant (RA) after survey completion that the participant screened positive for safety concerns, without revealing the survey contents. With the participant's permission, the RA will alert an appropriate member of the clinical staff, including social work, or Drs. [name], [name] or [name] such that they can connect the participant to resources to support their safety. During the study, should a subject express intent to harm themselves or others, we will contact a health or public safety professional. We will give only the subject's name, contact information, and why we feel he or she is at risk of harming themselves or others. This report will not be linked to his or her survey information. Subjects have the right to refuse to speak to the mental health professional. If the survey procedures results in the observation or suspicion of elder or child abuse, all research personnel will act in compliance with Illinois State law in regards to mandatory reporting of abuse.

Research staff will strictly adhere to the procedures for enrolling participants and collecting data as outlined by the investigators. At the conclusion of the study, all hard copy materials, with the exception of the consent copies, will be destroyed and electronic files will be deleted or archived in

password-protected files. Informed consent documents (paper or electronic) will be stored for at least 6 years following the completion of the study (defined by the last publication related to the study). Due to the small sample sizes associated with the pretest, the pretest data will not be made publicly available.

L. Payment

Caregivers enrolled in the pretest will receive \$25 in compensation for completion of the baseline interview (approximately 25 minutes) and \$25 in compensation each for completion of the one-week and 30-day follow-up surveys (approximately 30 minutes).

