Per Jennings' protocol, responses to each of the 4 items in the self-efficacy domain will be scored from 1 to 5 (1=strongly disagree to 5=strongly agree) and averaged. We will also assess caregiver self-efficacy for self-care using our measure from the CRx-2 trial. This measure derives from Bandura's Self-Efficacy theory: "How confident are you in your ability to find resources in your community that help you manage your [your care recipient's] health?" (5-point Likert scale "not at all confident" to "completely confident"). The pragmatic CRx-2 intervention was delivered, via the routine workflow, to adult patients by clinic staff or a nurse at discharge from an outpatient visit with no specific counseling. The proposed CRx-D intervention is more intensive (e.g. delivered by the research team with a brief education component, ongoing support, caregiver access to the Community Resource Finder). We therefore hypothesize that CRx-D may also promote general self-efficacy (a broader concept than Jennings' and the CRx-2 measure) and will explore this hypothesis by administering the Generalized Self-Efficacy Scale (range 10-40) at baseline and at follow-up.

Secondary and exploratory outcomes will also be measured longitudinally. These outcomes include:

**Psychosocial Outcomes** HRSNs will be assessed at baseline and follow-up using the CMS tool. The "core" tool includes 10 validated items to assess 5 needs domains: food, housing, interpersonal safety, transportation, and utility support. We will also include the domains "family and community support" (2 items) and "financial strain" (1 item). Each domain will be scored per CMS instructions. For follow-up surveys after 1 week, we will assess needs occurring in the interval since the last interview and, when a need is identified, during the past 30 days specifically. In addition to assessing unmet HRSNs, we will assess unmet caregiving-specific resource needs, using a tool we created from prior studies and our own qualitative work.

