## Aim 2:

Since the non-inferiority margin of 7.6 for satisfaction with care is a relative effect size of 0.3 standard deviations, this relative effect size will be used as the non-inferiority margin for the secondary outcome of discrimination.

More formally, non-inferiority testing will use linear regression:  $Y = \beta 0 + \beta 1 * T + \varepsilon$ , where Y is the outcome (satisfaction with care or discrimination) and T is the treatment group indicator. The 95% CI for  $\beta 1$  will be of particular interest.

Since a majority of participants were female and African American or Black, formal interaction testing was not performed. However, a sensitivity analysis was performed that restricted analyses to females.

An additional sensitivity analysis was performed that restricted the analysis to those who selfcompleted the 1-week survey online (vs. via phone interview).

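### The alert for a safety concern endorsed in the HRSN screening is tied to finishing the survey, so a concern endorsed in a web follow-up survey that is then abandoned could go unreported

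*Protocol*

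**What the plan says.** Final protocol, section K (Monitoring of safety), describes what happens when a participant endorses a safety concern in the HRSN screening: "REDCap will deliver an alert to the research assistant (RA) after survey completion that the participant screened positive for safety concerns". The alert does not reveal the answers. The next step needs consent: "With the participant's permission, the RA will alert an appropriate member of the clinical staff". Section K gives no time limit and does not mention unfinished surveys.

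Section K also has two routes that do not run through the REDCap alert. One is for stated intent: "should a subject express intent to harm themselves or others, we will contact a health or public safety professional". The other concerns abuse and opens "If the survey procedures results in the observation or suspicion of elder or child abuse", leading to mandatory reporting under state law.

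Four other places bear on the alert:

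- Section J (Potential risks and benefits): "Subjects will be informed that they can decline to answer any question and can terminate the survey or interview at any time". It also relies on the interviewer to watch for discomfort and to end the survey if needed.
- Section L (Payment) anticipates part-completed surveys, for which payment is not prorated.
- Section C (Methodology) makes the baseline survey interviewer-administered and allows phone or web follow-up: "self-administration of a web-based follow-up survey will also be offered".
- SAP, Aim 1, Psychosocial Outcomes: "HRSNs will be assessed at baseline and follow-up using the CMS tool". Interpersonal safety is one of the tool's five core domains.

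The Aim 2 SAP, under Additional Information, Clarification, Changes, shows that web self-completion took place. It reports a sensitivity analysis that "restricted the analysis to those who selfcompleted the 1-week survey online".

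**The concern.** The alert is worded as following the end of the survey. Someone who endorses a safety item and then stops has not reached that point. If a staff member is conducting the survey, that person is at least present when the item is answered. In a self-administered web survey nobody is, and the alert is the only stated means by which the study team would learn of the answer in time to respond.

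At stake is whether an endorsed concern about a participant's own safety is acted on or lies unread in a partial record. This does not affect any estimate or test in the SAP.

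**Working it through.** The documents state no figure to reproduce, so the check sets the passages side by side.

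1. **What the alert needs.** Section K requires an endorsed safety item in the HRSN screening and, read literally, a completed survey.

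2. **Can the first occur without the second?** Yes. Section J gives an unrestricted right to stop, and section L treats partial completion as something that will happen.

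3. **Is the tool used where nobody is present?** It can be. The SAP repeats it at follow-up, section C offers web follow-up, and the Aim 2 SAP shows that web completion occurred at 1 week.

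4. **What each situation yields under section K:**

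| Survey | Finished | Left unfinished after a safety item is endorsed |
|---|---|---|
| Interviewer-administered (baseline, phone follow-up) | Alert sent; staff member present | Alert not provided for; staff member present |
| Self-administered web follow-up | Alert sent; no stated way to seek permission | Alert not provided for; nobody present |

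Only the bottom right cell has neither an alert nor a person.

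5. **Do the other two routes cover that cell?** Not reliably. A participant must express intent to harm, or the survey procedures must lead to observed or suspected elder or child abuse. Both depend on staff hearing or noticing something. An adult caregiver who reports feeling unsafe does not clearly fall under either.

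6. **Can the number be estimated?** It would be

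   missed concerns = (web surveys carrying the HRSN tool) × (proportion endorsing a safety item) × (proportion of those abandoned afterwards).

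   The documents give none of the three terms. The schedule only caps the first. With full retention, follow-up surveys number 344 × 4 + 50 × 3 = 1,526. If the 7-day survey does not carry the tool, the cap is 344 × 3 + 50 × 2 = 1,132. How many were done online is not stated, and both proportions are unknown. The caps count occasions on which the web mode was available; they do not estimate missed concerns.

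**The case against.** The strongest reply is that section K may describe timing only. It says when the research assistant is told; it does not say that an unfinished survey produces no alert. The survey instruments and REDCap alert settings are not in the documents and may already handle partial records. This stands as a limit on the conclusion. It does not remove the point, because the written rule permits the literal reading and nothing else in the protocol excludes it.

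Other replies have force and narrow the point:

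- A reader might infer that the REDCap alert is the protocol's only safety route. It is not: the intent-to-harm and abuse routes do not depend on completion. The alert is the only stated trigger for concerns endorsed in the HRSN screening.
- A reader might infer that web completion itself defeats the alert. It does not. REDCap sends the alert without an interviewer, and the team holds a phone number and email address for each participant (sections F and H), so permission can be sought. What is missing is any statement of how and how soon.
- A reader might take section K's word screening to mean the baseline screen only, which would put 1,526 of 344 × 5 + 50 × 4 = 1,920 scheduled surveys (79%) outside the alert. That reading is strained. The SAP's reference list gives the tool repeated at follow-up the title of a screening tool, so the word more naturally covers every administration.
- A reader might blame the move to remote conduct. The original pretest protocol already offered web self-completion and the right to stop.

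The review of survey data for missingness in section I does not answer the point: it is data management, with no stated timing or safety purpose.

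**Conclusion.** The point holds in a narrow form. As written, section K does not provide for a safety concern endorsed in a self-administered web survey that is then abandoned, and such a concern could go unreported. A lesser gap is that the protocol does not say how permission is sought when a completed web survey raises the alert.

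The conclusion rests on two assumptions: that completion is read as a condition for the alert as well as its timing, and that web follow-up surveys carry the interpersonal safety items. The SAP supports the second in general terms, but its table of measures by time point is not in the text available.

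The documents do not support saying that endorsed concerns would in fact reach nobody, that those most at risk are the ones who break off, or that any particular number were missed. Any such number would rest wholly on assumed rates. This is a cheap improvement to a stated rule, of low to moderate priority.

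**What to change.** Reconcile section K with sections C and J of the final protocol and with the SAP's statement that the HRSN tool is repeated at follow-up. The revised text should do three things:

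- Make the alert independent of whether the survey is finished. A REDCap alert raised on the saved safety items is one example of how.
- State that the alert covers every administration of the HRSN tool, in every mode.
- State how permission is sought when no interviewer is present.

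The method of seeking permission and the response to an alert are for the sponsor to settle.

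The cost is a few sentences in section K and, if the system does not already work this way, a change of alert setting. The downside is a few extra alerts, including some triggered by answers that the participant later changes.
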